1H -MRS of GABA is technically more challenging and less studied. Although one early study reported that AD had significantly less occipital GABA than controls (Behar, 1999), two subsequent studies failed to find significant differences in mean brain GABA between AD and controls (Mason, 2006; Mon, 2012). Close inspection of the (Mason, 2006) data, however, suggest that GABA levels might differ by AW symptoms and history, while smoking history was found to also affect GABA level change over time. Intravenous ethanol reportedly decreases 1H -MRS GABA levels in social drinkers - interpreted as a reflection of alcohol-induced GABA receptor sensitivity leading to down regulation of GABA production and release. While, to our knowledge, no one has studied the effect of gabapentin on brain glutamate/GABA in alcoholics, gabapentin has been shown to increase brain GABA levels in humans by 1H -MRS both with acute (Cai, 2012; Petroff, 1996; Petroff, 2000) and chronic dosing (Kuzniecky, 2002). Remarkably, those with the lowest baseline levels (as might be found during AW) showed the most increase (Petroff, 2000). However, there has been very little published data on the effect of gabapentin on human brain glutamate levels. The only existing study found that a single gabapentin dose did not significantly impact glutamate levels in healthy controls (Cai, 2012). Data

generated from the proposed study could therefore add to the literature by elucidating the role of chronic gabapentin on glutamate levels in alcoholics.

In sum, although studies of glutamate and GABA in AD have not been completely consistent, they clearly demonstrate that 1) ¹H-MRS can be successfully applied to study this issue 2) that both systems might change over time with abstinence and/or with gabapentin treatment in a similar fashion to acamprosate (Umhau, 2010) and 3) there is a need to study these systems specifically in those with a history of alcohol withdrawal as a prediction of medication response and in the context of salient genetic differences.

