Lab and Genetic Assays: The CNL lab directed by [name] has 20 years of experience in measuring carbohydrate deficient transferrin (CDT) and currently runs a state-of-the-art HPLC based assay that is recognized by the IFCC as a candidate reference method (Helander, 2010). The analyte of interest is disialo-CDT as a percentage of total transferrin (%dCDT). Extensive quality control and proficiency testing is routinely performed. His lab also assays urinary Ethylglucuronide (EtG), a sensitive measure of any/low alcohol consumption using a Microgenics immunoassay which correlates highly with LC-MS. Qiagen DNA extraction kits are used to extract DNA from whole blood by a dedicated genetic technician in his lab, tested for DNA purity, and used in Taqman PCR analysis with specific probes and primers purchased from Life Science Technologies using a Step One analyzer (Applied Biosystems). His K05 funding allowed him to become proficient in this type of analysis (Anton, 2012) and he has genotyped hundreds of samples with various SNP's and VNTR's including the glutamate and GABA genes of interest (see background section).

Outcome Variables and Power Analyses: The primary drinking outcome variable will be the percent of subjects with no heavy drinking days (PSNHDD) as defined by Falk (2010), chosen because it is currently accepted by the FDA in its guidance for clinical trials and also is consistent with our prior work with gabapentin. However, other secondary drinking variables such as percent days abstinent, % heavy drinking days, and drinks per day, as well as craving (OCDS) and biomarkers (%dCDT and GGT) will be calculated and reported for completeness sake. Urinary riboflavin and pill counts will be used as measures of compliance and compared between groups while potentially serving to define compliers for independent analysis. PSQ, POMS, and MES will evaluate sleep quality, mood state, and medication effect differences between medication groups. Pre-randomization and week-3 brain glutamate and GABA levels will be calculated for each subject and their change will be the unit of measurement for the treatment effect mediator analysis (see below).

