Power has not been calculated for the exploratory genetic analyses. The genetic SNP's we have chosen to explore are not only indicated by the literature but also, importantly, have a reasonable genotypic distribution. Given our past work and HapMap data (see Preliminary Data section) we expect the distribution of both the *GABRA2* and *GM8* allele frequencies to be about 60:40 with not much difference between Euro-Caucasians and African Americans. This should provide a good balance between treatment groups. Modifier effects are likely to be observable if the effect size is moderate to large. In any case, this data will allow more appropriate power calculations for subsequent studies. Effects of genetic variation on brain glutamate/GABA are unknown and completely novel but as a main effect with 90 subjects (even accounting for drop-outs or unusable scans) the power to detect a gene by analyte effect should be sufficient if clinically meaningful.

Data Analysis Plan: *The PSNHDD (with baseline percent heavy drinking days as a covariate) will be analyzed with a multiple logistic regression with indicator coding medication group as the primary independent variable. All hypotheses (primary, secondary) will be assessed with likelihood ratios. Other possible pre-randomization variables, e.g. sex, smoking status, ADS score, pre-randomization CIWA-Ar score, etc. will be evaluated as possible covariates in the final analysis. Missing data (assuming monotonicity) will be imputed as heavy drinking days. In addition, the relapse time-course will be analyzed by GEE techniques for the full treatment X time factorial design. Secondary outcome variables, e.g. other drinking variables, OCDS, POMS, PSQ index, MES and biomarkers (%dCDT and GGT), will be analyzed as either mixed models (SAS PROC MIXED) or in GEE analyses (SAS GENMOD) depending upon the nature of the variable (parametric or categorical).*

Change in glutamate and GABA levels will be analyzed as a mixed model (SAS PROC MIXED) with time as a within subject variable and medication group as between subject variables. Significant interactions will be interpreted with simple effects and main effects will be assessed in the absence of the interaction. If sex and smoking status (reported by some to effect brain GABA levels), or pre-randomization CIWA-Ar score are found to significantly influence glutamate or GABA levels, or if their inclusion reduces residual variance, they will be included in the model as covariates.

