
In order to assess the degree to which changes in brain GABA and glutamate account for drinking outcomes, neurochemical variables (as difference scores) will be entered into the main logistic regression model. A reduction in the significance of the main treatment effect or the treatment by time interaction will be suggestive of a mediation effect. Path analysis will be used to test the significance of the indirect path from treatment to GABA/glutamate levels to relapse status and/or other drinking measures.

Timeline: Since our staff is trained in all procedures and scales are digitalized, the first 3-4 months will be used for medication production, database building, and data collection computer tablet study specific program production. In the first year we will screen/randomize 38/18 subjects and then 57/27 subjects in year 2-3 and 38/18 subjects in year 4. The last five months will be used for data analysis and publication production.

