Interpretations and Future Directions: While this study will focus on gabapentin efficacy in those with a history of AWS, it is possible that it might have anti-craving and reinforcement effects *independent of effects based on AWS history*. Since this proposal will not include those without a history of AWS we will not be able to address the issue of broader efficacy directly. However, using exploratory analysis on craving effects, reasons for drinking and medication effects scales, as well as sleep, we might discover mediators of treatment efficacy that could be studied in expanded populations in the future. Also, baseline levels of brain glutamate/GABA cannot be compared with levels in alcohol dependent individuals without a history of AW. Nevertheless, the ability to relate drinking outcome to changes in these levels and ability to relate the efficacy of gabapentin to glutamate/GABA brain changes would still be salient and important, as would the pharmacogenetic exploration. Since the complete understanding of brain glutamate/GABA levels as measured by ¹H-MRS is evolving, it is possible that those with AW might have less glutamate and more GABA prior to randomization since the pools measured might exist mostly in the intra-cellular space due to auto-regulatory mechanisms and/or sequestration, but still might change during treatment. The directionality of the effect will not negate the potential to observe changes based on gabapentin treatment and the relationship of those changes to efficacy. It will add data to the growing literature that could, in fact, assist in correct interpretation of the localization of these brain neurotransmitters. Furthermore, even if gabapentin is not found efficacious, the difference in brain glutamate and GABA levels change over time, especially in relationship to relapse status, would still add new information about AW biology and prognosis *that could be useful for future drug development*. The collection of DNA on all subjects will allow future explorations including deeper sequencing and epigenetic/regulatory changes of the candidate genes proposed, as well as exploration of other genetic variation that might emerge in relationship to relapse and medication response. *If these results are positive, future studies might investigate more specific pharmacological treatment matching between those with and without a history of alcohol withdrawal symptoms.*

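### The mediation model uses GABA/glutamate change scores without naming the pre-dose level as a covariate, so a prognostic starting level would bias the mediator coefficient

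*Combined protocol and SAP*

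**What the plan says.** Under Outcome Variables and Power Analyses, the pre-randomization and week-3 metabolite levels are computed for each participant, and "their change will be the unit of measurement for the treatment effect mediator analysis". The mediation paragraph of the Data Analysis Plan repeats this: "neurochemical variables (as difference scores) will be entered into the main logistic regression model". The main logistic model is fitted "with baseline percent heavy drinking days as a covariate". Further covariates are left open: "Other possible pre-randomization variables, e.g. sex, smoking status, ADS score, pre-randomization CIWA-Ar score, etc. will be evaluated as possible covariates". Pre-dose GABA and glutamate are not among the examples.

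Two readings of mediation follow. One is informal: "A reduction in the significance of the main treatment effect or the treatment by time interaction will be suggestive of a mediation effect". The other is a path analysis of the "indirect path from treatment to GABA/glutamate levels to relapse status", described in one sentence with no equations. The separate mixed model for the metabolites uses both scans, but it addresses the effect of drug on metabolite, not the link from metabolite to relapse.

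The background on spectroscopy notes that, for GABA under gabapentin, "those with the lowest baseline levels (as might be found during AW) showed the most increase".

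**The concern.** The stated question is whether changes in the metabolites account for drinking outcome. Someone who starts low tends to rise more and someone who starts high tends to fall more, so a change score carries information about the starting level. If the starting level is itself prognostic, the coefficient on change picks that up, and a test of that coefficient is no longer a test of change alone. Randomization does not protect it, because change is measured after randomization and is not itself randomized.

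The plan expects the first leg, drug to metabolite, to be detected almost always. The mechanistic conclusion therefore turns on the second leg, which is the coefficient at risk. The Significance section would use such a result to argue that other drugs with similar effects on GABA and glutamate could be useful. A proper indirect-effect test would inherit the same bias, so the problem is separate from the informal rule about reduced significance.

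**Working it through.** **Inputs from the documents.** 45 per arm; at most 10% of scans lost, so about 40 per arm (45 × 0.9 = 40.5); drug effect on glutamate change d = .95; treatment odds ratio 3.2 for not relapsing (study 1, withdrawal-positive participants); likelihood-ratio tests.

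**Assumptions not in the documents.** Two-sided .05; correlation ρ between the two scans of .3, .5 or .7; equal SDs at both scans; pre-dose odds ratio of 2 per SD (0.5 in the reverse direction); 25% of placebo participants with no heavy drinking day at the mean baseline; scans without error unless stated. In the power runs the direct log-odds effect of treatment was 0.3. Baseline percent heavy drinking days was left out of the tabulated runs because the documents give no effect for it.

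**1. The plan's own figure.** Power for the first leg is Φ(d√(n/2) − 1.96). With n = 45 and d = .95 this is Φ(4.51 − 1.96) = .995; with d = .6 it is Φ(2.85 − 1.96) = .81. The plan states above .99 and .8, so both reproduce. The documents give no figure for the mediation test.

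**2. Algebra.** Let B be the pre-dose level, F the week-3 level and D = F − B, each level with SD 1. Within an arm:

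- cov(B, D) = ρ − 1 and var(D) = 2(1 − ρ).
- corr(B, D) = −√((1 − ρ)/2), which is −.59, −.50 and −.39 at ρ = .3, .5 and .7.
- The slope of B on D is (ρ − 1)/(2(1 − ρ)) = −1/2, whatever ρ is.

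If B shifts the log-odds by c, leaving B out moves the coefficient of D by about −c/2. For an odds ratio of 2, c = 0.69 and the shift is about −0.35. The simulated mean was −0.34.

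**3. Change has no effect.** Simulation, 2,000 trials per setting, 40 per arm. The indirect path counts as significant when both legs are. Entries are for ρ = .3 / .5 / .7.

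| Pre-dose level and outcome | Change score only | of these, benefit sign (% of all trials) | Pre-dose level added |
|---|---|---|---|
| Not prognostic | 5.4 / 5.2 / 5.4% | 2.6 / 2.6 / 2.7% | 5.6 / 5.6 / 5.6% |
| OR 2, low GABA or high glutamate predicts relapse | 36.1 / 27.1 / 17.7% | 0.0 / 0.2 / 0.2% | 5.1 / 5.1 / 5.0% |
| OR 2, reverse direction | 36.0 / 26.5 / 18.2% | 36.0 / 26.5 / 18.2% | 5.6 / 5.6 / 5.5% |

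Separate runs put the planned rate at about 17-37% and the adjusted rate at about 5-7%. The bias does not depend on ρ, but D varies less as ρ rises, so the bias is detected less often.

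**4. The informal rule.** With 45 per arm and no effect of change, the treatment effect lost significance after D was added in 11-12% of trials when B was not prognostic. This became 26-35% in the reverse direction and 1-3% in the direction where low GABA or high glutamate predicts relapse.

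**5. Real mediation.**

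- *Week-3 level drives outcome, OR 2.5 per SD.* Since F = D + B, B has the same effect as D at fixed change, and the planned coefficient is roughly halved (0.92 to about 0.43). Power with 40 per arm is about 26-53% as planned against 73-93% adjusted. With 45 per arm it is 57 / 45 / 29% against 95 / 90 / 77%.
- *Change effect of OR 2 plus a baseline effect twice as large in log-odds, 45 per arm.* The algebra gives 0.69 − 1.39/2 ≈ 0, that is, cancellation. Power is about 6% as planned against 76 / 67 / 50%.
- *Pure change drives outcome.* The planned model is better by about 9-11 points. With 45 per arm and OR 2 it is 92 / 83 / 62% against 78 / 72 / 55%, a gap of 14, 11 and 7 points.

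**6. Scan error.** With assumed reliability .6, true correlation .7 and pre-dose OR 3, the false-path rate is about 12% as planned and 16% adjusted. At OR 2 it is about 8% and 9%.

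**The case against.** The strongest reply is that the plan asks about change, and if change alone drives relapse the planned model is the more powerful one. That stands. The power loss in step 5 belongs to a different truth, in which the week-3 level or the starting level also matters.

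Three further points stand:

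- The text does not exclude the pre-dose level. The covariate list is open-ended, the path model is not written out, and the path sentence speaks of levels. The fair statement is that the adjustment is not specified.
- The documents do not say that the pre-dose level predicts relapse. They name relapse prediction as something to examine and cite associations of glutamate with cognition and craving. The remark on low starting levels concerns GABA only.
- Adjustment is not a complete cure. The spectroscopy section accepts fits with uncertainty up to 20%, and with noisy scans and a high scan correlation the advantage can vanish or reverse.

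A reader might also infer that the Interpretations section accepts an indirect path of either sign as a finding: "The directionality of the effect will not negate the potential to observe changes based on gabapentin treatment and the relationship of those changes to efficacy". In context that sentence concerns the direction of the measured neurotransmitter levels. It sets no rule for the sign of a mediation path.

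None of this removes the core point. Followed as written, the rule mixes change with starting level, and nothing in the plan fixes in advance whether the adjustment will be made.

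**Conclusion.** The concern holds as a conditional risk. It needs a prognostic pre-dose level, a correlation between baseline and change, and a drug effect on the metabolite. Without the first, the planned test keeps its 5% level. With a pre-dose odds ratio of 2 per SD and the assumptions listed above, a significant indirect path arises in about 17-37% of trials in which change plays no part, against about 5-7% after adjustment.

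It would be tempting to read 17-37% as the chance of a false claim that GABA or glutamate mediates efficacy. The documents do not support that. If low GABA or high glutamate predicts relapse, the false path has the benefit sign in well under 1% of trials, and the practical harm is masked mediation or a path of the wrong sign. A false efficacy signal needs the opposite prognostic direction. The Interpretations section allows that pre-randomization levels might be reversed, but it does not say that they would predict relapse.

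The analysis of heavy drinking and the mixed model for drug effect on the metabolites are unaffected. This is a cheap improvement to a secondary mechanistic analysis.

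**What to change.** In the mediator definition under Outcome Variables and Power Analyses and in the mediation paragraph of the Data Analysis Plan, state that:

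- each metabolite's pre-dose level is a covariate wherever its difference score enters, that is, in the logistic model and in both path equations (using the week-3 level with the pre-dose level as covariate gives the same mediator test);
- the mediation conclusion rests on that adjusted indirect path;
- the unadjusted difference-score model is reported as a sensitivity analysis;
- the path is read as mediation of efficacy only if its sign is in the direction of benefit.

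The cost is a few sentences and one model term per metabolite. No new data are needed, because the pre-dose scan is already collected. The price is a modest loss of power, about 9-11 points, if pure change drives relapse. The report should also say that scan error limits what the adjustment can achieve.

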Proton Magnetic Resonance Spectroscopy (¹H-MRS) for Glutamate and GABA: This will occur prior to randomization (see above) and again at week 3 (window between days 17-24) of study medication between 2-4 hours after the last gabapentin/placebo dose to standardize acute dosing effects. Subjects will be breathalyzed prior to the scan and need to be zero (or will be rescheduled ASAP), and, if smokers, the time of last cigarette will be recorded. In an ongoing trial we have found no problems with imaging (fMRI) clinical trial participants twice (baseline/week 3) – very few have to be rescheduled due to drinking and some subjects find it intriguing. Each scan takes about 60 minutes and uses the following protocol: A structural scan will be taken for ¹H-MRS voxel placement and tissue segmentation (256 sagittal slices; 1mm thick/50% gap). The ACC voxel for ¹H-MRS will be placed on midsagittal T1-weighted images, anterior to the genu of the corpus callosum, with the ventral edge of the voxel aligned with the dorsal edge of the genu and a voxel size of 3 x 2.5 x 2.5 cm³ will be selected (consistent with Umhau, 2010 and Mon, 2012). Following auto-shimming, single-voxel water-suppressed ¹H-MRS spectra will be acquired using a Point Resolved Spectroscopy (PRESS) sequence: Repetition Time (TR) = 2000ms; Echo Time (TE) = 40ms; number of averages = 256); an unsuppressed water spectrum will be co-acquired (TE = 40ms, number of averages = 16), scaled for partial volume effects and relaxation, and used as a concentration reference. This sequence has been shown to

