Only metabolites with fitting uncertainties (Cramer-Rao Lower Bound values) < 20% of SD in the LC Model output will be retained for analysis. LC Model includes standardized zero filling, Fourier transformation, and automated phase, baseline, and eddy current correction. To address variability in within-voxel tissue composition we will: 1) co-register T₁-weighted images to their scout images and correct for b₁ field bias, 2) extract and segment T₁-weighted images into partial volume maps of gray matter (GM), white matter (WM), and CSF using FMRIB Software Library (FSL) tools, 3) match the coordinates and size of the ¹H-MRS voxel with the segmented images and extract the tissue fractions within the voxel using FSL tools, 4) correct the raw values obtained from the LC model (scaled to water) for CSF and coil loading (Michaelis, 1993), and 5) calculate each participant's GM to brain matter (BM) ratio (i.e., GM:BM = GM/[GM+WM]) for use as a covariate in statistical analyses. This calculation will be made separately for each metabolite of interest because the spatial region that each metabolite is localized to is not the same due to the chemical shift artifact. The particular displacement of a given metabolite's localization region is determined by the metabolite's chemical shift divided by the product of the strength of the gradient used to localize the voxel and the gyromagnetic ratio for protons. For each metabolite, in each participant, we will match the coordinates and size of the voxel (accounting for chemical shift displacement) with the segmented images and extract the tissue fractions using FSL tools. Metabolite concentration estimates will be corrected for T₁ and T₂ relaxation effects using established literature values (Mlynarik, 2001; Wansapura, 1999) and scaled to water. Following this procedure we have produced the following example spectra:

FIGURE 3. LC Model Spectra for Glutamate

[figure not shown]
[figure not shown]

FIGURE 4. LC Model Spectra for GABA

We have run 6 healthy controls *through the PRESS MRS sequence* and found a mean (SD) glutamate, as a ratio to water, of 7.66 (1.24) or as a ratio to creatine, 1.38 (0.15). *We have run an additional 7 healthy controls through the MEGA-PRESS MRS sequence and found a mean (SD) GABA, as a ratio to water, of 1.75 (0.19). These values are consistent with published levels (where there is a range of values based on quantification method and reference analyte).*

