A statistical power calculation was conducted using data from our past two studies (background section) using the treatment effect in subjects with a DSM-IV history of AW on the PSNHDD outcome variable. With 45 subjects per medication group (total N=90) the power to detect the gabapentin treatment effect on PSHDD is between .83 (study 1 calculation) and .98 (study 2 calculation). While significant covariate effects in our earlier studies have not been observed with this outcome variable, additional power analysis using Monte Carlo simulation (n=500) in the presence of covariates modeled, (e.g. pretrial drinking, OCDS, ADS, etc.) on our previous studies was conducted. Power values comparable to those in the simpler analysis were found in all cases ranging from .81 to .87 (study 1) to .95 to .99 (study 2).

The statistical power calculation for gabapentin's effect on brain glutamate change from baseline to week-3 is based on the work of Umhau (2010), the study design closest to our own, where an acamprosate-induced change in brain glutamate levels (vs. placebo) was detected with an effect size of .95. *The power to detect a similar gabapentin vs. placebo difference in the current proposal with an n=45/group is in excess of .99 with the ability to detect an effect size as low as $d = .6$ with power of .8. Since the reported effect of gabapentin on GABA is quite large (Cai, 2012; Kuzniecky, 2002; Petroff, 1996; Petroff, 2000) the power to detect a gabapentin vs. placebo difference with an n=45/group is in excess of .9. Given this large statistical power, an expected maximal 10% attrition due to inadequate scans should not materially affect our ability to detect a medication effect on glutamate or GABA. Additionally, there is likely to be sufficient variation in both medication response and brain glutamate/GABA level change to allow acceptable use of a mediation analysis to examine the effect of this glutamate/GABA change on treatment response.*

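### The mediation check compares treatment significance between models that may be fitted to different numbers of people, because there is no rule for participants without two usable scans

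*Combined protocol and SAP*

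**What the plan says.** All references are to the Approach section of the combined protocol and SAP.

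- **Mediation rule (Data Analysis Plan).** To judge whether metabolite change explains the drinking result, "neurochemical variables (as difference scores) will be entered into the main logistic regression model". Lower significance for the treatment effect, or for treatment by time, is then taken to suggest mediation. A path analysis of the indirect effect follows; neither its analysis set nor its handling of missing scans is given.
- **Mediator (Outcome Variables and Power Analyses).** The mediator is the change from the pre-randomization scan to the week-3 scan.
- **Routes to a missing score (Proton Magnetic Resonance Spectroscopy).** Only metabolite values that pass a fitting-uncertainty limit "will be retained for analysis". The second scan has a window of days 17 to 24. Breath alcohol also matters: "Subjects will be breathalyzed prior to the scan and need to be zero (or will be rescheduled ASAP".
- **Expected loss (Outcome Variables and Power Analyses).** The plan says that "an expected maximal 10% attrition due to inadequate scans should not materially affect our ability to detect a medication effect" on the metabolites. That is a statement about power for the scan outcome.
- **Missing-data rule (Data Analysis Plan).** "Missing data (assuming monotonicity) will be imputed as heavy drinking days". Week-16 drinking is also sought from people who drop out, and data continue to be collected for intent-to-treat after medication stops.

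**The concern.** Between them, the drinking rules give essentially all 90 participants a primary outcome. None of them can supply a metabolite value. A logistic regression omits anyone with a missing covariate unless told otherwise, so the model containing the change scores would by default be fitted to a subset of the people in the main model.

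A smaller sample gives a larger p-value on average even when the treatment coefficient does not move. The plan's screening criterion is exactly such a rise, so lost scans can be mistaken for evidence of mechanism. Linking gabapentin's efficacy to brain glutamate and GABA change is one of the trial's stated scientific purposes, and a false hint would carry into later work. If the two metabolites fail quality control in different people, the glutamate and GABA models would also rest on different subsets.

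**Working it through.** **Inputs**

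- From the plan: "With 45 subjects per medication group (total N=90"); scan loss of at most 10%; treatment odds ratio 3.2 (study 1, participants positive for alcohol withdrawal); and, for glutamate, "an acamprosate-induced change in brain glutamate levels (vs. placebo) was detected with an effect size of .95". On testing: "All hypotheses (primary, secondary) will be assessed with likelihood ratios".
- Assumed, because the text does not give them: two-sided alpha of 0.05; placebo success of 20% or 30%, which with odds ratio 3.2 gives 44% or 58% on gabapentin.

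**1. The plan's own figures.** For a two-sample t test the noncentrality is d × √(n/2).
- n = 45: 0.95 × √22.5 = 4.51, power 0.994; 0.6 × √22.5 = 2.85, power 0.804. Both stated figures (above .99, and .8) are reproduced.
- After 10% loss (40.5 per arm): power 0.99 at d = 0.95 and 0.76 at d = 0.6. The statement that loss is immaterial is fair for the scan outcome at d = 0.95. It does not address the mediation comparison.

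**2. Number with a score.** 90 × 0.90 = 81. If both metabolites enter one model and fail independently at 10% each, the loss is 1 − 0.9² = 19%, leaving about 73.

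**3. Effect of loss alone.** With an unchanged coefficient, z shrinks by √0.90 = 0.949.
- z = 2.0 becomes 1.897: p goes from 0.046 to 0.058.
- z = 2.2 becomes 2.087: p goes from 0.028 to 0.037.

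**4. Effect of adding a score that differs between arms but does not affect drinking.** With equal arms, the squared correlation of arm and score is r² = d²/(d² + 4). At d = 0.95, r² = 0.9025/4.9025 = 0.184, so z shrinks by about √(1 − 0.184) = 0.903 (a linear-model approximation). This exceeds the shrinkage from losing 10% of the scans.
- z = 2.2 becomes 2.2 × 0.903 = 1.99 (p = 0.047) with no scans lost.
- With both effects it becomes 2.2 × 0.903 × 0.949 = 1.89 (p = 0.059).

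**5. Simulation.** 45 per arm, odds ratio 3.2, 9 of 90 scan pairs lost at random, no effect of the score on drinking (so zero mediation), likelihood-ratio tests. The table gives the share of significant trials in which treatment loses significance once the score is added. The unequal-sample column counts trials significant on all 90; the other counts trials significant in the reduced set. Ranges span the two placebo rates and repeated runs.

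| Effect of arm on score | 90 against 81 | Same 81 in both models |
|---|---|---|
| none | 8% to 12% | 1% to 2% |
| d = 0.95 | 19% to 24% | 15% to 19% |

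Unequal samples therefore add about 7 to 10 points in the first row and 4 to 5 in the second. At d = 0.95 with no scans missing, 13% to 17% still lose significance.

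With a baseline covariate and two change scores unrelated to arm, the figures were about 10% against 2% to 3%. Refitting without any score on the reduced set already lost significance in 9% to 10%, while the treatment log-odds barely moved (1.41 against 1.43). In that setting the lost subjects produce the signal.

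**The case against.** The strongest reply is that missing scans are the smaller part of the problem. The plan expects gabapentin to move the metabolites, and under that premise most of the false signal comes from reading a p-value change after adding a covariate correlated with arm. This stands. A reader might infer from the no-effect row that a same-participant rule brings the false signal down to 1% or 2%; at the plan's d = 0.95 it does not.

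Second, the significance drop is described only as suggestive, and the path analysis is the formal test. This also stands and limits the harm. A separate check with true mediation found that extra scan loss among relapsers did not noticeably bias the path estimates. The path analysis still has no stated way of handling missing scans.

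Third, the plan never says that incomplete cases are dropped. Correct: 81 against 90 is the default behaviour of the model, not a stated mismatch. The defect is an unstated analysis set.

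Fourth, loss may be small. The plan reports that very few participants in an ongoing twice-scanned trial needed rescheduling because of drinking, and failures of the fitting limit may already be within the 10%. On the other side, the 10% is worded for inadequate scans and does not mention dropout before day 17. Neither argument fixes a number.

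Finally, under random loss the odds ratio does not shrink, so a reader shown the estimates rather than the p-values would see no attenuation. That is a reason to change the criterion.

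**Conclusion.** The point holds as a gap in the mediation analysis, of modest size. At the plan's own maximum of 10% loss, taken as random, unequal samples add about 7 to 10 percentage points of spurious loss of significance if gabapentin leaves the metabolite unchanged, and about 4 to 5 points at d = 0.95. These figures rest on odds ratio 3.2, assumed placebo success of 20% to 30%, two-sided 0.05 and zero mediation.

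Larger or selective loss would change them. In the extreme and purely assumed case where the 10% lost are all placebo relapsers, 36% to 40% of significant trials lose significance; losing gabapentin relapsers instead could hide mediation.

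Two stronger readings are not supported. A reader might infer that missing scans by themselves would lead the trial to conclude mediation, but the formal test is the path analysis and the larger weakness is the p-value criterion. A reader might also infer damage to the efficacy result, but the primary logistic analysis needs no scan and is unaffected.

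**What to change.** In the mediation paragraph of the Data Analysis Plan:

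1. State that the logistic models with and without change scores are fitted to the same participants: either those with both scans usable for that metabolite, or all 90 with missing scan values multiply imputed using arm, pre-dose level and drinking outcome.
2. Use the same missing-data method in the path analysis.
3. Base the mediation conclusion on the indirect effect with a confidence interval, and drop the change in p-value as a criterion. Item 1 alone is not enough.
4. Report the number without a change score by arm, reason and relapse status.
5. Keep the treatment effect on all 90 as the efficacy result, not as the comparator for mediation.

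The cost is wording and one extra model fit per metabolite, with no new data. The price is about 10% fewer people in the comparison or, with imputation, one added modelling assumption.
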